7.2 SUBJECT DISCONTINUATION/WITHDRAWAL FROM THE STUDY

Subjects are free to withdraw from participation in the study at any time upon request. As well, an investigator may discontinue or withdraw a subject from the study for the following reasons:

- If the subject's wound is open at follow-up week 1, the subject will be exited. They will be noted as having completed their study requirements.
- Significant study intervention non-compliance
- If any adverse event (AE), laboratory abnormality, or other medical condition or situation occurs such that continued participation in the study would not be in the best interest of the subject

- Anytime continued participation in the study is not in the best interest of the subject
- Disease progression which requires discontinuation of study participation
- Signs/symptoms of infection which require antibiotic therapy that persist more than 1 visit at a time or more than twice (non-consecutive visits) during the 12-week Treatment Phase.
- If the subject meets an exclusion criterion (either newly developed or not previously recognized) that precludes further study participation
- If the subject's site withdraws from the study
- If the Sponsor decides to stop the study

The reason for subject discontinuation or withdrawal from the study will be recorded on the appropriate eCRF. Subjects who sign the informed consent form and are randomized but do not receive the study intervention may be replaced.

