6.1.2 UTILIZATION AND ADMINISTRATION

IMPORTANT: These recommendations are designed only to serve as a general guideline. They are not intended to supersede institutional protocol or professional clinical judgement concerning patient care.

6.1.2.1 RECOMMENDED INSTRUCTIONS FOR USE OF THE PNEUMATIC SHORT LEG WALKERS (BOOT) & SUPPLIES (SOC DRESSINGS)

During the Screening Phase of the study, all subjects will have SOC products applied by the investigative site at the weekly visits. They will be then instructed on how to change their dressings on a daily basis. After randomization, only subjects who are randomized to the SOC cohort will continue daily dressing changes. Those subjects in either the AMNIOEXCEL Plus or Apligraf cohorts will only have their dressings changed weekly at follow-up visits until the investigator determines that their wound has closed. If the wound closes on or before week

12, offloading (if previously utilized for that subject) will continue without dressings during the follow-up period.

The off-loading boot/protective device and SOC dressings to be used in this study will be provided by the Sponsor through a specific distributor. The off-loading boot/protective device will only be used by subjects who require offloading throughout the Screening and Treatment (i.e., those subjects with study ulcers located on the plantar or lateral surfaces of the foot or any location experiencing weight-bearing or shear forces *as determined by the Investigator*). These subjects will wear the boot up to their exit from the study. The boot will be applied to the subject's foot on top of the dressings.

Application of the dressings & boot by the Investigator:

1. Gently remove any dressing previously applied to the wound and clean the area with a gentle cleanser.
2. If appropriate, debridement and hemostasis will be performed. (Note: in this study only sharp debridement will be used)
3. During Screening and for SOC-randomized subjects: Instruct the subject on the proper way to change dressing
 - a. Inspect the wound and perform study assessments as directed elsewhere
4. Apply normal saline gel to the thickness of a coin.
5. Cover the gel with a foam dressing.
6. Secure the foam dressing with conforming roller gauze.
7. Cover the roller gauze with Coban.
8. For subjects who have ulcers that require offloading, apply the boot.

Daily Changing of the Dressings by the Subject:

1. Remove boot, if applicable
2. Gently remove dressings

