6.4 STUDY INTERVENTION COMPLIANCE

Subject compliance will be assessed by the site via standard didactic and interview methods. An initial training on dressing changes and application of the boot with the subject will occur on Screening Visit 1 (-12 weeks \pm 3 days). Compliance and subsequent (i.e., refresher) training will occur on each follow-up visit until the patient completes the study. This is shown in detail in the Table 2: Schedule of Activities.

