Subjects enrolled in this study must have an ABI of between 0.65 and 1.2. NOTE: An ABI result obtained within 3 months of the first screening visit may be used to qualify the potential subject for participation in this study.

- **Toe Pressure**
The blood pressure within the toe is measured in much the same way as obtaining blood pressure in the arm. Briefly, use a Doppler probe to determine that a pulse is present at the base of the great toe. Apply the correct sized cuff to the great toe and place the Doppler probe distal to the cuff (the pulse should be audible). Inflate the cuff sufficiently to occlude the pulse and slowly release the cuff. Note the pressure, in mmHg, when the pulse returns. To participate in this study, the potential subject must have a toe pressure greater than 50mmHg in the foot with the study ulcer.
- **Transcutaneous Oxygen Level (TcPO₂)**
TcPO₂ is a measure of oxygen delivery to a local area. A special machine must be used to assess TcPO₂. Briefly, electrodes for the sensor will be placed onto the intact skin close to the study ulcer. The oxygen sensor then can read the oxygen content of the tissue and reports this as mmHg pressure. Each site should refer to the equipment's manual for specific and correct instructions for use. For this study, potential study candidates must have a TcPO₂ greater than 40 mmHg.
- **Treatment Compliance Review (Screening Visit 1 & 2, Randomization, Weeks 1 - 12)**
Screening Visits 1 & 2: The site will instruct the subject on how to perform daily dressing changes and apply the offloading boot, if offloading is used.

Randomization Visit: For subjects randomized to the SOC cohort, the site will instruct the subject on how to perform daily dressing changes and apply the offloading boot, if offloading is used. For those subjects randomized to the AMNIOEXCEL Plus or Apligraf cohorts, only the offloading boot will be discussed, if applicable. Subjects in these arms do not change their dressings at home.

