On subsequent visits, the site will ask the subject whether they are performing the dressing changes and/or offloading, as applicable. To appropriately assess compliance, the site will ask the subject if they are wearing their boot at all times except when bathing or sleeping. Further, when the offloading boot is removed, the site will examine the exterior of the boot for signs of wear and the interior for evidence of depressions in the boot liner. The site will document their assessment of compliance on the appropriate eCRF. *Note: The site should replace worn liners as necessary.*

- **Debridement (Screening Visit 1 & 2, Randomization, Weeks 1 - 11)**
Debridement is the removal of dead, damaged, or devitalized tissue to improve the healing potential of the remaining healthy tissue. Removal may be sharp, mechanical, chemical, or autolytic (self-digestion); however, in this study only sharp debridement will be used.
- Following debridement, hemostasis should be obtained with pressure. The use of silver nitrate sticks, styptic pencils or electro-cautery should be avoided as these coagulation methods induce further tissue damage.
- **Photography (All Study Visits)**
For this study, imaging software created by Tissue Analytics, Inc. will be used to collect images of the subjects' ulcers.

Using the app provided by Tissue Analytics, Inc., sites will take an image of the study ulcer. These images will be used to: 1) document the status of the wound and 2) use planimetry to calculate the area of the open wound. Photographs of the wound will be taken after the dressings are removed, the wound is cleansed, debrided, and hemostasis has been achieved, if debridement is performed. The app will automatically measure the wound area; the site does not need to enter this information into the EDC system.

The site will use the imaging methodology set forth in the current imaging vendor's procedure manual. Imaging should be conducted in such a manner as to eliminate (to the best of the site's ability) any identifying information such as tattoos, birthmarks, etc.

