9.5. Missing Data

For primary efficacy evaluation of data points, the last available observation (LOCF) will be used. In the analyses of using the planimetry data, the last available planimetric value will be used for a discontinued subject. All subjects discontinued during the treatment period and before 100% wound closure during the treatment phase of the study will not be replaced and will be considered treatment failures for evaluating the primary and secondary endpoints.

10. Description of Other Variables and Analyses

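### An undefined non-compliance exit, scored as failure, can bias the AMNIOEXCEL Plus versus SOC closure difference, because daily home dressing is a duty of SOC only

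*Protocol*

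**What the plan says.** - **Exit rule.** Protocol section 7.2 states that "an investigator may discontinue or withdraw a subject from the study for the following reasons", and one listed reason is "Significant study intervention non-compliance". No number of missed dressings, boot hours or visits is given, and no arm is named.
- **Who judges.** Section 6.3 describes an open-label study. Section 6.4 says "Subject compliance will be assessed by the site via standard didactic and interview methods"; section 8.2 adds inspection of the boot for wear.
- **Duty by arm.** Section 6.1.2 says "After randomization, only subjects who are randomized to the SOC cohort will continue daily dressing changes". Of the two allograft arms, section 8.2 says "Subjects in these arms do not change their dressings at home". At later visits "the site will ask the subject whether they are performing the dressing changes and/or offloading, as applicable". The boot question is common to all arms where offloading is used: "the site will ask the subject if they are wearing their boot at all times except when bathing or sleeping".
- **After exit.** Section 7.1 names a single situation in which a subject stays in the study once intervention has ended, namely a closed wound. A subject exited with an open wound has no later closure assessment.
- **Scoring.** Under SAP section 9.5, subjects who discontinue during treatment before full closure "will be considered treatment failures for evaluating the primary and secondary endpoints". LOCF (protocol section 9.4.5, SAP section 9.1) gives the same result when the last observation is an open wound.
- **Comparison affected.** AMNIOEXCEL Plus versus SOC is one of the two primary comparisons (protocol section 9.4.5).

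**The concern.** In an ITT comparison, how well subjects keep to a regimen is part of that regimen's effect. A subject who misses home dressings may still heal by Week 12, and that outcome could be observed. The plan allows it to be replaced by an imputed failure, on an undefined judgement by site staff who know the arm. The Investigator who may exit the subject also assesses the primary endpoint.

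All arms can fail on boot wear and attendance. Only SOC subjects can fail on daily home dressing changes. If that extra duty leads to extra exits, and some of those subjects would have closed, SOC closure is understated and the AMNIOEXCEL Plus versus SOC difference is overstated. The Apligraf comparison does not share this asymmetry, since neither allograft arm changes dressings at home.

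**Working it through.** **The plan's own figure.** With 38 per arm and 90% closure, protocol section 9.2 gives a 95% half-width of 13.5%.

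- Difference between two arms: 1.96 × √(2 × 0.9 × 0.1 / 38) = 13.49%, which matches.
- Single closure rate, as the text labels it: 1.96 × √(0.9 × 0.1 / 38) = 9.5%, which does not match.

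So 13.5 points is the planned precision of a between-arm difference, and it serves as the yardstick below.

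**Home dressing changes.** Twelve weeks have 7 × 12 = 84 days. The site applies dressings at Day 0 and at Weeks 1 to 11, which is 12 visits. That leaves 84 − 12 = 72 home changes at most in SOC, fewer if the wound closes early, and none in the allograft arms.

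**Shift in SOC closure.** Let k be the excess of SOC subjects exited open for non-compliance, and q the probability that such a subject would have closed. The documents give neither, so both are assumed. SOC closure falls by k × q / 38.

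| Excess SOC exits (k of 38) | q = 0.5 | q = 0.9 |
|---|---|---|
| 0 | 0 | 0 |
| 1 | 1.3 points | 2.4 points |
| 2 | 2.6 points | 4.7 points |
| 4 | 5.3 points | 9.5 points |

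The planned 20% attrition is 0.20 × 38 = 7.6 subjects per arm, so four such exits would fit within it.

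**Shift in the difference when both arms have exits.** With exit shares e(SOC) and e(allograft), the difference moves by q × (e(SOC) − e(allograft)). A positive value favours AMNIOEXCEL Plus.

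| e(SOC) | e(allograft) | q = 0.5 | q = 0.9 |
|---|---|---|---|
| 10% | 0% | +5.0 | +9.0 |
| 10% | 5% | +2.5 | +4.5 |
| 10% | 10% | 0 | 0 |
| 5% | 10% | −2.5 | −4.5 |

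**Effect on the test.** Take equal true closure q in both arms, 38 per arm, exits in SOC only, and a normal approximation to the pooled two-proportion test. The chance of a significant result favouring AMNIOEXCEL Plus is 2.5% with no excess exits. With a 5% excess it is 4.1% (q = 0.5) or 8.6% (q = 0.9). With a 10% excess it is 6.4% or 19.7%.

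For the last figure, the rates are 0.90 and 0.90 × 0.90 = 0.81, with mean 0.855. The null standard error is √(2 × 0.855 × 0.145 / 38) = 0.0808, and the alternative standard error is √((0.09 + 0.1539) / 38) = 0.0801. Then z = (1.96 × 0.0808 − 0.09) / 0.0801 = 0.85, with upper tail 19.7%.

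**The case against.** A reader might infer that the rule does bias closure against SOC, or that dressing non-compliance is an exit route open to SOC alone. The documents support neither.

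- **The criterion is arm-neutral on its face.** Boot wear is reviewed wherever offloading is used. Allograft subjects must keep the weekly dressing dry (sections 6.1.2.2 and 6.1.2.3), and a missed visit costs them a product application. Only missed daily changes are specific to SOC. This stands.
- **Direction is not established.** Bias needs both an excess of SOC exits and exited subjects who would have closed, and neither rate is given. The limits in section 7.1 on withholding allografts for infection are an exit path of those arms alone and could push the other way. This stands.
- **Screening reduces the risk.** All subjects change dressings daily at home during the screening period. Inclusion criteria 2 and 8 require willingness and ability and allow a relative or friend to help. Exclusion criterion 14 removes those judged unable to comply. Section 6.4 provides retraining at each visit. These lower the likely number of exits but do not bring it to zero.
- **Detection is partly planned.** Exit reasons are summarised by arm (SAP section 10.2.1) and compared by Fisher's exact test (SAP section 11.1.3); compliance is summarised by visit (SAP section 10.4). These can show an imbalance but cannot recover the lost outcomes. The PP analysis drops major violators, so it does not recover them either.
- **Removing one reason would not be enough.** Section 7.2 also allows exit for a newly met exclusion criterion, and criterion 14 is inability to comply. This stands, and the fix has to cover both routes.
- **The trial is not powered for testing**, as both documents say. A shifted point estimate and interval mislead all the same, and a CMH test at the two-sided 0.05 level is still planned.

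**Conclusion.** The concern holds as a risk. An undefined, unblinded exit decision ends outcome assessment and is scored as failure, and one component of compliance is required of SOC only. The AMNIOEXCEL Plus versus SOC difference can be biased by this, most plausibly against SOC, but the documents fix neither size nor direction.

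Under assumption, 1 to 4 excess SOC exits out of 38, with 50% to 90% who would have closed, move SOC closure by 1.3 to 9.5 points, against a planned half-width of 13.5 points for a difference. Equal exits move it by 0, and excess allograft exits reverse the sign. A change is worth making because the missing outcomes are avoidable and the remedy is cheap.

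**What to change.** 1. **Protocol section 7.2.** State that non-compliance alone, whether through its own bullet or through the newly met exclusion bullet via criterion 14, does not end study participation or outcome collection. Keep willing subjects on the scheduled visits through Week 12 and the confirmation visits. This concerns attendance and outcome recording only, not treatment.
2. **Deviations.** Record such non-compliance as a protocol deviation under section 10.1.9, and deal with it in the PP population.
3. **SAP sections 9.1 and 9.5.** Use the observed closure status of these subjects in ITT.
4. **Reporting.** Show non-compliance, and any exits that follow from it, by arm, with home dressing and offloading separate.
5. **Sensitivity analysis.** Add one that does not force non-compliance exits to failure, for example by varying their closure probability from 0 to 1 separately in each arm.

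The cost is wording in both documents and some further visits that are already in the schedule. Some of these subjects will still stop attending, so the sensitivity analysis is needed in any case. SAP section 12 reports the photograph review as already done; if subject visits are also complete, items 4 and 5 remain feasible.

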7.3 LOST TO FOLLOW-UP

If a subject does not return for a study-related visit, the subject is not automatically considered lost-to-follow-up (LTFU). The site should proceed with the following prior to designating a subject as LTFU:

1. Contact the subject via phone
 - a. Use the primary phone; if the subject's phone has been disconnected utilize any other phone numbers ever provided.
 - b. Contact the subject's Primary Healthcare Physician for any contact information
2. Contact the subject via certified mail
 - a. Send a certified letter to the subject's most recent address.

Only after the subject fails to respond to the certified letter may the subject be considered LTFU.

Subjects who are discontinued, lost-to-follow-up or withdrawn and who have not achieved complete wound closure by week 12 of the Treatment Phase of the study will not be replaced.

[Intentionally Blank]

8 STUDY ASSESSMENTS AND PROCEDURES

8.1 STUDY PROCEDURE OVERVIEW

The below list is an overview of procedures or information to document at each visit. Where added, information in parentheses relate to the procedures listed in Table 2: Schedule of Activities at the beginning of the protocol. The detail about these procedures is found in the following section.

8.1.1 SCREENING VISIT 1 (-2 WEEKS [14 DAYS] ± 3 DAYS)

1. Conduct Informed Consent Process (Informed Consent & HIPAA)
2. Review Eligibility Criteria (Inclusion/Exclusion)
3. Collect Demographics & Medical History from Patient
4. Perform Physical Examination
5. Perform Vascular Perfusion Assessment (if most recent ABI is greater than 3 months old or no assessment is present in subject's medical records)
 - a. ABI, Toe Pressure, or TcPO₂ (ABI is preferred)
6. Discuss Requirements for Study Compliance (Treatment Compliance Review)
7. Perform Sharp Debridement on Study Ulcer, if needed (Debridement)
8. Collect Images of the DFU (Photography)
9. Perform Ulcer Assessments
10. Treat Subject Using SOC Procedures (Standard of Care)
11. Train subject on wound cleansing and dressing changes
12. Apply Boot, if applicable (Boot Application)
13. Document Concomitant Medications & Procedures (ConMeds and Other Procedures)

8.1.2 SCREENING VISIT 2 (-1 WEEKS [7 DAYS] ± 3 DAYS)

1. Review Eligibility Criteria (Inclusion/Exclusion)
2. Review Study Compliance with the Subject (Treatment Compliance Review)
3. Perform Sharp Debridement on Study Ulcer, if needed (Debridement)
4. Collect Images of the DFU (Photography)
5. Perform Ulcer Assessments
6. Treat Subject Using SOC Procedures (Standard of Care)
7. Apply Boot, if applicable (Boot Application)
8. Document Adverse Events
9. Document Concomitant Medications & Procedures (ConMeds and Other Procedures)

8.1.3 RANDOMIZATION VISIT (DAY 0) – POINT OF ENROLLMENT

1. Review Eligibility Criteria (Inclusion/Exclusion)
2. Review Study Compliance with the Subject (Treatment Compliance Review)
3. Perform Sharp Debridement on Study Ulcer, if needed (Debridement)
4. Collect Images of the DFU (Photography)
5. Perform Ulcer Assessments
6. Randomize Subject (Randomization)

7. Treat per Randomization Group (SOC + Treatment)
 - a. AMNIOEXCEL Plus Cohort (Discontinue *Daily* Dressing Regimen)
 - b. Apligraf Cohort (Discontinue *Daily* Dressing Regimen)
 - c. Standard of Care Cohort
8. Apply Boot, if applicable
9. Train subject on maintenance of dressing and when to call/return to the study site
10. Document Adverse Events
11. Document Concomitant Medications & Procedures (ConMeds and Other Procedures)

8.1.4 WEEK 1 (7 ± 3 DAYS) THROUGH WEEK 11 (77 ± 3 DAYS); UNSCHEDULED VISITS

1. Review Study Compliance with the Subject (Treatment Compliance Review)
2. Collect MRU Data for the Previous Week (MRU Assessment)
3. Perform Sharp Debridement on Study Ulcer, if needed (Debridement)
4. Collect Images of the DFU (Photography)
 - a. Important: If the subject has been randomized to the Apligraf cohort, the non-adherent layer should not be removed at the Week 1 timepoint (See section 6.1.2.3 RECOMMENDED INSTRUCTIONS FOR USE OF APLIGRAF). Sites do not need to image the wound at Week 1 if the subject is in the Apligraf cohort; however, if the non-adherent layer disengages from the wound of its own volition, imaging may occur. In this latter case, care should be taken to not disturb the Apligraf.
5. Perform Ulcer Assessments
6. Treat per Randomization Group (SOC + Treatment)
 - a. AMNIOEXCEL Plus Cohort (Weekly Dressing Changes, Only)
 - b. Apligraf Cohort (Weekly Dressing Changes, Only)
 - c. Standard of Care Cohort
7. Apply Boot, if applicable
8. Document Adverse Events
9. Document Concomitant Medications & Procedures (ConMeds and Other Procedures)

8.1.5 WEEK 12 (84 ± 3 DAYS)

1. Review Study Compliance with the Subject (Treatment Compliance Review)
2. Collect MRU Data for the Previous Week (MRU Assessment)
3. Collect Images of the DFU (Photography)
4. Perform Ulcer Assessments
5. Apply Boot, if applicable
6. Document Adverse Events
7. Document Concomitant Medications & Procedures (ConMeds and Other Procedures)

8.1.6 FOLLOW-UP VISITS - WEEKS 13 & 14 (91 & 98 ± 3 DAYS)

1. Collect MRU Data for the Previous Week (MRU Assessment)
2. Collect Images of the DFU (Photography)
3. Perform Ulcer Assessments
4. Apply Boot, if applicable
5. Document Adverse Events

6. Document Concomitant Medications & Procedures (ConMeds and Other Procedures)

IMPORTANT: If the subject’s wound is open at Follow-up visit 1 (e.g., week 13), the subject is exited from the study and is marked as having completed their study requirements. The site will note why they believe the wound is still open.

8.2 ASSESSMENTS

The following assessments will occur for each subject consented into the study according to the Study Procedure Overview above:

- **Informed Consent (Screening Visit 1) – ALWAYS THE FIRST ACTIVITY**
Please see the section dedicated to the informed consent process in section 10.1.1 of this document.
- **Eligibility (i.e., Inclusion/Exclusion; Screening Visits 1 and 2 and Randomization [Day 0])**
The Investigator will review medical records and query the subject as needed to determine if the subject meets the inclusion and exclusion criteria for the study. Inclusion/exclusion review will be complete on Randomization (Day 0) after the Investigator reviews the amount of wound closure after debridement. The site will enter whether the subject meets each applicable criterion into the EDC system.
- **Demographics & Medical History (Screening Visit 1)**
The site will collect the subject’s date of birth, gender, ethnicity, race, and will assess nicotine use. Diabetic history will be noted. Diabetes type, date of diagnosis, date of most recent HbA1c test, and %HbA1c will be documented. A separate HbA1c test does not need to occur unless the subject’s most recent test is greater than 3-months (90 days) from the date of Screening Visit 1. Documentation of other medical conditions will be made based on body systems (e.g., cardiovascular, dermatologic, endocrine, gastrointestinal, etc.).
- **Physical examination (Screening Visit 1)**
Height and weight, along with blood pressure, will be documented. Sites will document any abnormalities in any of the following: extremities, neurologic, cardiovascular, musculoskeletal, dermatological and/or other systems. A vascular perfusion assessment (either the ABI, systolic pressure of the great toe, or TcPO₂) will be noted. Sites will document whether or not the subject has multiple DFUs.
 - **Vascular Perfusion Assessment (Screening Visit 1, if necessary)**
Perform one of the following:
 - **ABI (Preferred Assessment)**
The ABI is the ratio of the brachial pressure (i.e., blood pressure in the arm) to the blood pressure in the ankle. Briefly, the blood pressure is obtained in the arm (brachial) and then obtained in a similar manner in the ankle. To obtain the ratio (i.e., index), divide the systolic pressure from the ankle by that obtained in the arm.

$$ABI = \frac{Systolic\ Pressure_{ankle}}{Systolic\ Pressure_{arm}}$$

Subjects enrolled in this study must have an ABI of between 0.65 and 1.2. NOTE: An ABI result obtained within 3 months of the first screening visit may be used to qualify the potential subject for participation in this study.

- **Toe Pressure**
The blood pressure within the toe is measured in much the same way as obtaining blood pressure in the arm. Briefly, use a Doppler probe to determine that a pulse is present at the base of the great toe. Apply the correct sized cuff to the great toe and place the Doppler probe distal to the cuff (the pulse should be audible). Inflate the cuff sufficiently to occlude the pulse and slowly release the cuff. Note the pressure, in mmHg, when the pulse returns. To participate in this study, the potential subject must have a toe pressure greater than 50mmHg in the foot with the study ulcer.
- **Transcutaneous Oxygen Level (TcPO₂)**
TcPO₂ is a measure of oxygen delivery to a local area. A special machine must be used to assess TcPO₂. Briefly, electrodes for the sensor will be placed onto the intact skin close to the study ulcer. The oxygen sensor then can read the oxygen content of the tissue and reports this as mmHg pressure. Each site should refer to the equipment's manual for specific and correct instructions for use. For this study, potential study candidates must have a TcPO₂ greater than 40 mmHg.
- **Treatment Compliance Review (Screening Visit 1 & 2, Randomization, Weeks 1 - 12)**
Screening Visits 1 & 2: The site will instruct the subject on how to perform daily dressing changes and apply the offloading boot, if offloading is used.

Randomization Visit: For subjects randomized to the SOC cohort, the site will instruct the subject on how to perform daily dressing changes and apply the offloading boot, if offloading is used. For those subjects randomized to the AMNIOEXCEL Plus or Apligraf cohorts, only the offloading boot will be discussed, if applicable. Subjects in these arms do not change their dressings at home.

On subsequent visits, the site will ask the subject whether they are performing the dressing changes and/or offloading, as applicable. To appropriately assess compliance, the site will ask the subject if they are wearing their boot at all times except when bathing or sleeping. Further, when the offloading boot is removed, the site will examine the exterior of the boot for signs of wear and the interior for evidence of depressions in the boot liner. The site will document their assessment of compliance on the appropriate eCRF. *Note: The site should replace worn liners as necessary.*

- **Debridement (Screening Visit 1 & 2, Randomization, Weeks 1 - 11)**
Debridement is the removal of dead, damaged, or devitalized tissue to improve the healing potential of the remaining healthy tissue. Removal may be sharp, mechanical, chemical, or autolytic (self-digestion); however, in this study only sharp debridement will be used.
- Following debridement, hemostasis should be obtained with pressure. The use of silver nitrate sticks, styptic pencils or electro-cautery should be avoided as these coagulation methods induce further tissue damage.
- **Photography (All Study Visits)**
For this study, imaging software created by Tissue Analytics, Inc. will be used to collect images of the subjects' ulcers.

Using the app provided by Tissue Analytics, Inc., sites will take an image of the study ulcer. These images will be used to: 1) document the status of the wound and 2) use planimetry to calculate the area of the open wound. Photographs of the wound will be taken after the dressings are removed, the wound is cleansed, debrided, and hemostasis has been achieved, if debridement is performed. The app will automatically measure the wound area; the site does not need to enter this information into the EDC system.

The site will use the imaging methodology set forth in the current imaging vendor's procedure manual. Imaging should be conducted in such a manner as to eliminate (to the best of the site's ability) any identifying information such as tattoos, birthmarks, etc.

Important: If the subject has been randomized to the Apligraf cohort, the non-adherent layer should not be removed at Week 1 (See section 6.1.2.3 RECOMMENDED INSTRUCTIONS FOR USE OF APLIGRAF). Sites do not need to image the wound at Week 1 if the subject is in the Apligraf cohort; however, if the non-adherent layer disengages from the wound of its own volition, imaging may occur. In this latter case, care should be taken to not disturb the Apligraf.

- **Ulcer Assessments**

- **Screening Visits 1 & 2**

- The location of the ulcer will be noted. Extent of ulceration (i.e., tunneling, tendon exposure, etc.), exudate assessment, and infection assessment. **Ulcer area will always be assessed using the post-debridement (or pre-debridement if no debridement was performed) photographs.**

- **All Study Visits following Screening Visits 1 & 2**

- Exudate assessment, infection assessment, and investigator assessment of wound closure will be collected.

- **Completion of Study Assessment (Follow Up Visits)**

- Sites will assess completion status of the subject and will make a determination about the status of the wound (closed or not).

- **Standard of Care, Offloading (Screening Visits 1 & 2, Randomization, Weeks 1-11 as applicable)**

- Sites will apply SOC materials and boots according to the procedures laid out in section 6.1.2 and will document in the EDC system what materials were used. The site will document that a weekly kit was used and that they provided materials and training to the subject as applicable.

- **Randomization (Day 0)**

- Sites will review eligibility criteria a final time and document that the subject has met these criteria in the EDC system. The EDC system will provide the site with the appropriate cohort based on a pre-determined randomization scheme. The site will proceed with applying the appropriate treatment products based on the mandated cohort for that subject.

- **Investigational Product, Offloading (Randomization, Weeks 1-11, as applicable)**

- Sites will apply investigational product and SOC materials and boots, if applicable, according to the procedures laid out in section 6.1.2 and will document in the EDC system what materials were

used. Sites will document the product used (AMNIOEXCEL Plus or Apligraf), the product's lot number, and method of securing. The site will also document that a weekly kit was used, that they provided materials and training to the subject as applicable.

- **MRU Assessment (Weeks 1 – 12, Follow-Up Weeks 1 & 2)**

As applicable, the site will document the following for the subject's previous visit week:

- Any and all DRG Codes, using ICD-10, that were or would be applied to the subject
- The associated CPT codes and modifiers for those CPT codes

- **Concomitant Medications (All Study Visits)**

Sites will query the subjects at each visit about any medications they are currently taking. Only medications that (1) affect the wound area, (2) affect the limb, (3) are related to the treatment of the wound, (4) are being used to treat any AEs that develop during this study, will be documented. The name, indication/reason for use, dose, route, frequency, start/stop date, and whether the medication is being used to treat any adverse events will be noted.

- **Assessment of Adverse Events (All Study Visits after Screening Visit 1)**

After the initial screening visit, sites will report full information on those AEs possibly, probably, or definitely-related to the investigational product or study procedure. Other AEs that are not related or unlikely related will only have basic information collected (Stop and Start Date). If these AEs change in relationship (e.g., an ongoing unrelated AE becomes possibly related) full information will be collected.

Sites will collect the AE onset date and a description of the event. The sites will then make a determination as to whether the AE is Serious or not and will grade its severity marking it as either (1) mild, (2) moderate, or (3) severe. For any treatment or procedure-related SAEs that are graded as (1) possibly, (2) probably or (3) definitely-related, the site will also indicate whether the event is anticipated or unanticipated. Definitions of these terms can be found in the following section of the protocol.

Sites will also note the action taken (none, medication given, hospitalization required, surgical intervention, or other), and the outcome of the AE (resolved with or without sequelae, death, ongoing, or other). If available, an adverse event resolution date will be noted. The site will also make a determination as to whether the AE caused the subject to discontinue participation in the study.

See Section 8.3 below for more information on AE definitions and procedures.

